3.3 Justification for Dose

FMP250 is 250cc of healthy fecal homogenates and a standard size offering for FMT prepared by OpenBiome. It is also the standard dosage used for FMT treatment of *C. difficile* infection. Single dose delivery of FMP250 was chosen as per our previous pilot study and due to supply cost constraints.

3.4 End of Study Definition

A subject is considered to have completed the study if he or she has completed all phases of the study including the last visit, at week 12 depending on treatment assignment or the last scheduled procedure shown in the Schedule of Assessments (SoA), Section 6.1. The end of the study is defined as completion of the last visit or procedure shown in the SoA in the trial globally.

4. Subject Selection

4.1 Study Population

Subjects with a diagnosis of ulcerative colitis who meet the inclusion and exclusion criteria and are willing to undergo a standard of care colonoscopy to confirm their eligibility to participate in this study.

4.2 Inclusion Criteria

1. Male or Female \geq 18 years of age.
2. Documentation of prior history of mild to moderate UC.
3. Endoscopy confirmed active UC \geq 15 centimeters at day 0 screening colonoscopy.

- a. As defined by a total Mayo scoring of 4-10 with an endoscopic sub-score ≥ 1 and a stool frequency or rectal bleeding sub-score of ≥ 1 .
4. Patients must have a descending intact colon.
5. Patients taking steroid or biologic therapy must be on a stable dose for 4 weeks prior to screening and maintained throughout the trial.
6. Eligible patients willing to undergo serological and fecal screening testing prior to FMT to document baseline status:
 - a. Urine Testing
 - i. Pregnancy test (women with childbearing potential)
 - b. Blood Testing
 - i. B-HCG (research purposes)
 - ii. CBC, ESR, CRP, and BMP (standard of care)
 - iii. HIV, type I and II (standard of care)
 - iv. Hepatitis A B C Profile (standard of care)
 - v. RPR (*treponema pallidum*) (research purposes)
 - vi. CMV IgM (standard of care)
 - vii. Quantiferon-TB (standard of care)
 - c. Stool Testing
 - i. Calprotectin (standard of care)
 - ii. Clostridium Difficile Toxin PCR (standard of care)
 - iii. Ova & parasites (standard of care)
 - iv. Gastrointestinal Pathogen PCR Panel (standard of care)
 1. *Campylobacter* species
 2. *Plesiomonas Shigelloides*
 3. *Salmonella* Species
 4. *Vibrio* Species
 5. *Vibrio cholerae*
 6. *Yersinia Enterocolitica*
 7. Enterotoaggregative *E. coli* (EAEC)
 8. Enteropathogenic *E. coli* (EPEC)
 9. Enterotoxigenic *E. coli* (LT/ST)
 10. Shigalike toxin producing *E.coli* I (STX/ST2)
 11. *Cryptosporidium*
 12. *Cyclospora cayetanensis*
 13. *Entamoeba cayetanensis*
 14. *Giardia*
 15. *Adenovirus* F 40/41
 16. *Astrovirus*
 17. *Norovirus* GI/GII
 18. *Rotavirus* A
 19. *Sapovirus*
 20. *GID* PCR INTERP

7. Patients must discontinue anti-rCDI antibiotics (e.g. vancomycin, fidaxomicin) 48 hours prior to FMT delivery procedure.

4.3 Exclusion Criteria

1. Biopsy proven Crohn's disease
2. UC patients with severe disease (defined as a total mayo score >10)
3. Clinical complications requiring emergent management (e.g. stricture, bowel obstruction, perforation and/or abscess)
4. Concurrent *C. difficile* or other infections
5. Primary sclerosing cholangitis
6. Prior history of FMT
7. Treatment for malignancy within past 5 years
8. Active or latent tuberculosis
9. Clinically meaningful laboratory abnormalities
 - a. Hb: < 8
 - b. ALT: greater than 3x the ULN (upper limit of normal)
10. History of anaphylactic reactions to food allergens or allergy to psyllium husk
11. Pregnancy or lactation
12. Probiotic use in the 4 weeks prior to screening and for the duration of the trial
13. Subject having any other condition that, in the opinion of the investigator, would jeopardize the safety or rights of the subject participating in the study, would make it unlikely for the subject to complete the study, or would confound the study.

4.4 Lifestyle Considerations

During this study, subjects will not be specifically instructed to restrict any lifestyle considerations. However, a 24-hour diet recall will be conducted during our screening clinic visit (day -28 to -3) with a clinical nutritionist/registered dietician or study physician at Jill Roberts IBD Center in efforts to accurately observe and record each subject's daily eating patterns. See **Section 6.1.1.** for more details.

4.5 Screen Failures

Screen failures are defined as participants who consent to participate in the clinical trial and have potentially been randomized into a treatment assignment but do not meet all inclusion criteria, specifically the endoscopy scoring for active disease at the day 0 standard of care colonoscopy. A minimal set of screen failure information is required to ensure transparent reporting of screen failure participants, to meet the Consolidated Standards of Reporting Trials (CONSORT) publishing requirements and to respond to queries from regulatory authorities. Minimal information includes demography, screen failure details, eligibility criteria, and any serious adverse event (SAE).

Individuals who do not meet the criteria for participation in this trial (screen failure) at the day 0 standard of care colonoscopy may be rescreened at a later time.

4.6 Strategies for Recruitment and Retention

This clinical trial will recruit potential participants from the Jill Roberts Center for Inflammatory Bowel Disease and related facilities of New York Presbyterian Hospital/Weill Cornell Medical Center where our investigators are members of the medical staff. The Jill Roberts Center for IBD is a high-volume practice, led by our investigator [name], with over 4,000 IBD patients and with a full-time clinical research team dedicated to investigator-initiated studies. Our clinical research personnel are responsible for the recruitment, screening, enrollment and allocation of participants in study groups. We anticipate to identify and screen approximately 150 potential study participants from within our practice but will subsequently enroll 135 subjects. We expect the accrual rate to be approximately 40 to 50 subjects per year.

Recruiting efforts for this study will not target potential participants based on their gender, race, or ethnicity. Recruitment strategies will include submitting a summary of the study to clinicaltrials.gov and to the Jill Roberts IBD Center Website: <https://jillrobertsibdcenter.weillcornell.org/research-and-clinical-trials/clinical-trials>.

Subjects will not be compensated with financial incentives at any point during the study.

5. Registration Procedures

5.1 Subject Registration (WCM only)

Subjects will be registered within the WRG-CT as per the standard operating procedure for Subject Registration.

5.2 Subject Registration (Sub-sites)

Not Applicable.

6. Study Procedures

6.1 Schedule of Assessments

Table 1. Schedule of trial events

	Day -28 to -3	Day 0	Day 1	Wk 2	Wk 4	Wk 6	Wk 8	Wk 10	Wk 12	Off Study ^d
Informed consent	X									
Demographics	X									
Medical history	X									
Concurrent medication	X								X	
Treatment Randomization	X									
Physical exam	X				X		X		X	
Vital signs + Height + Weight	X				X		X		X	
B-HCG (serum pregnancy test) (research purposes)	X									

Urine Pregnancy Test (standard of care and research purposes)		X ^c					X			
CRP: C-Reactive Protein (standard of care)	X*						X			
ESR: Erythrocyte Sedimentation Rate (standard of care)	X*						X			
CBC ^a (standard of care)	X*						X			
CMP ^b (standard of care)	X*						X			
Blood: HIV screen (standard of care)	X*									
Blood: Hepatitis A B C Profile (standard of care)	X*									
Blood: RPR (Treponema pallidum) (research purposes)	X									
Blood: CMV IgM (standard of care)	X*									
Blood: Quantiferon-TB (standard of care)	X*									
Fecal Calprotectin (standard of care)	X*						X			
Stool: Ova & parasites (standard of care)	X*									
Stool: Clostridium difficile Toxin PCR (standard of care)	X*									
Stool: Gastrointestinal Pathogen PCR Panel ^e (standard of care)	X*									
Screening Colonoscopy (standard of care)		X								
Blinded (Investigational or Placebo) FMP250 Treatment		X								
Follow-up Flex sigmoidoscopy (standard of care)							X			
Blinded Investigational FMP250 (research purposes)							Placebo group only			
Blinded Placebo FMP250 (research purposes)							Investigational group only			
Mucosal Biopsy Collection (research purposes)		X					X			
Blood and Stool Collection (research purposes)	X-----X				X		X		X	
Follow-Up Phone calls (research purposes)			X	X		X		X		X
Diet Recall with Clinical Nutritionist or study MD (research purposes)	X									
Psyllium Fiber Supplements (research purposes)		X-----X								
Adverse event evaluation		X -----X								

*: These standard of care laboratory tests must be done during the screening period. However, if the subject consents on page 5 of the informed consent form, recent laboratory results may instead be used if the subject had them conducted within 2 weeks of signing consent.

- a: Complete Blood Count (WBC count, RBC count, Hb, Hct, platelet count)
- b: Comprehensive Metabolic Panel (glucose, calcium, sodium, potassium, CO₂, chloride, BUN, Creatinine)
- c: Urine pregnancy test (women of childbearing potential) as standard of care for colonoscopy
- d: Off-study evaluation for the following year.
- e: Gastrointestinal Pathogen GI Panel (Campylobacter species, *Plesiomonas Shigelloides*, *Salmonella* Species, *Vibrio* Species, *Vibrio cholerae*, *Yersinia Enterocolitica*, Enteroaggregative *E. coli* (EAEC), Enteropathogenic *E. coli* (EPEC), Enterotoxigenic *E. coli* (LT/ST), Shigalike toxin producing *E.coli* I (STX/ST2), *Cryptosporidium*, *Cyclospora cayetanensis*, *Entamoeba Cayetanensis*, *Giardia*, *Adenovirus F 40/41*, *Astrovirus*, *Norovirus GI/GII*, *Rotavirus A*, *Sapovirus*, GID PCR INTERP)

6.1.1 Screening Visit (Days -28 to -3)

- Informed consent
- Medical history
- Medication history
- Physical exam
- Blood Testing
 1. B-HCG (research purposes)
 2. CBC, ESR, CRP, and CMP (standard of care) *
 3. HIV, type I and II (standard of care) *
 4. Hepatitis A B C Profile (standard of care) *
 5. RPR (treponema pallidum) (research purposes)
 6. CMV IgM (standard of care) *
 7. Quantiferon-TB Gold Plus, 1 Tube (standard of care) *
- Stool Testing
 1. Calprotectin (standard of care) *
 2. Clostridium Difficile Toxin PCR (standard of care) *
 3. Ova & parasites (standard of care) *
 4. Gastrointestinal Pathogen PCR Panel (standard of care) *
 - *Campylobacter* species
 - *Plesiomonas Shigelloides*
 - *Salmonella* Species
 - *Vibrio* Species
 - *Vibrio cholerae*
 - *Yersinia Enterocolitica*
 - Enteroaggregative *E. coli* (EAEC)
 - Enteropathogenic *E. coli* (EPEC)
 - Enterotoxigenic *E. coli* (LT/ST)
 - Shigalike toxin producing *E.coli* I (STX/ST2)
 - *Cryptosporidium*
 - *Cyclospora cayetanensis*
 - *Entamoeba Cayetanensis*
 - *Giardia*
 - *Adenovirus F 40/41*
 - *Astrovirus*
 - *Norovirus GI/GII*
 - *Rotavirus A*
 - *Sapovirus*

- GID PCR INTERP
- Treatment Randomization (blinded to clinician and subject)
 1. Fiber treatment groups must receive psyllium dietary supplements (2 teaspoons/day) to begin on day -3
- Diet Recall with Clinical Nutritionist/Registered Dietician or study MD
 1. A subjective dietary record will be assessed anytime during the screening period (day -28 to -3), either by an clinic or phone call consult, in conjunction with the registered dietitian (RD). This meeting will aim to capture detailed information about food and beverages consumed over a certain (typical) period of time as an estimate of usual intake. The discussion may begin with the RD asking the subject "Could you please walk me through a typical day in terms of what you eat and drink from the time you wake up until you go to sleep?" The RD may then assess what the subject normally eats on a regular weekday, and give them the opportunity to tell them a few different options they might have for breakfast, lunch and dinner as well as snacks (if their days vary). They may also review what kinds of fruits and vegetables they consume most commonly, as well as get a sense of how much added sugar is likely in the subject's diet.
- Stool and blood samples taken for research purposes
 - This can be collected anytime during the screening period or on the day of the screening colonoscopy, prior to blinded FMT treatment, but if the subject is randomized to receive psyllium fiber, then this should be collected before day -3 when they begin the fiber supplementation.

*: These standard of care laboratory tests must be done during the screening period. However, if the subject consents on page 5 of the informed consent form then recent laboratory results may instead be used if the subject had them conducted as standard of care within 2 weeks of signing consent.

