Study Description:	A double-blind, randomized, placebo-controlled clinical trial examining the efficacy and safety of Fecal Microbiota Transplantation (FMT) and high fiber supplementation in patients with active mild to moderate Ulcerative Colitis (UC). All enrolled subjects will provide serological, stool and mucosal specimen at each clinic visit to help further define the alterations in microbial profiles and immune cell function in response to psyllium fiber after FMT treatment.
Sample Size:	N=135, 45 subjects per study arm
Enrollment:	This study will enroll 135 subjects and screen up to 150 subjects.
Study Population:	All male and female participants at least 18 years of age with prior history of mild to moderate Ulcerative Colitis and willing to undergo standard of care colonoscopy to assess active disease for study eligibility.
Enrollment Period:	2019-2023
Study Design:	This is a randomized, double-blind, placebo-controlled clinical trial with the following treatment assignments: 
1. Investigational FMP250 (one-time) at week 0
a. Subjects in this group will also blindly receive placebo FMP250 at week 8 by flexible sigmoidoscopy.2. Investigational FMP250 (one-time) at week 0 + Psyllium fiber (2x/day for 8 weeks)
a. Subjects in this group will also blindly receive placebo FMP250 at week 8 by flexible sigmoidoscopy.3. Placebo FMP250 (one-time) at week 0 with or without Psyllium fiber (2x/day for 8 weeks)
a. Subjects in this group will also blindly receive investigational FMP250 at week 8 by flexible sigmoidoscopy. Subjects will blindly receive the investigational or placebo FMP250 treatment only if they meet all inclusion and exclusion criteria during the day 0 screening colonoscopy. Subjects will receive a follow-up phone call or return for a clinic visit every 2 weeks post-FMT until week 12. At week 8 post-FMT, all subjects will be evaluated by flexible sigmoidoscopy in the clinic. Stool and blood samples will be collected for research from subjects at day 0 prior to FMT, week 4 post-FMT, week 8 post-FMT, and

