3.1 Overall Design

Hypothesis: A high fiber diet will promote the engraftment of healthy donor microbiota and increase the efficacy of FMT in UC patients. If successful, this proposal will help us to define the role for dietary fiber supplementation in promoting microbial determinants of successful FMT and enhance the clinical efficacy of FMT for UC.

Study Phase: II

Study Design: Double-blinded, randomized, placebo-controlled clinical trial

Study Drug: FMT Lower Delivery Microbiota Preparation (FMP250)

Study Arms:

Group 1: Investigational FMT

- Subject will receive investigational FMT once at day 0 colonoscopy
- Subject will receive placebo FMT once at week 8 flexible sigmoidoscopy
- Observed for 12 weeks

Group 2: Investigational FMT + psyllium fiber

- Subject will receive investigational FMT once at day 0 colonoscopy
- Fiber supplementation of 1 teaspoon 2x/day for 8 weeks
- Subject will receive placebo FMT once at week 8 flexible sigmoidoscopy
- Observed for 12 weeks

Group 3: Placebo FMT with or without psyllium fiber

- Subject will receive placebo FMT once at day 0 colonoscopy
- Half of subjects will be randomized to receive fiber supplementation of 1 teaspoon 2x/day for 8 weeks
- Subject will receive investigational FMT once at week 8 flexible sigmoidoscopy
- Observed for 12 weeks

Site:

Weill Cornell Medical Center / New York Presbyterian Hospital (Clinical Facility)

- The Jill Roberts Inflammatory Bowel Disease Center at David H. Koch Center

Weill Cornell Medicine Belfer Research Building (Research Laboratory Facility)

- The Jill Roberts Institute for Research in Inflammatory Bowel Disease

Methods to Minimize Bias:

1. Randomization Bias
 - a. A series of randomized blocks of fixed size will be generated with a 1:1:1 allocation ratio. This will provide assurance that after a given block has completed subject enrollment, there will be the same number of subjects assigned to each of the three study arms. Additionally, the specific number of subjects within any randomization block (i.e., block size) will be blinded to all investigators to avoid any risk for unblinding treatment arms prior to the primary endpoint evaluation.
2. Unblinding Bias

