3.2 Scientific Rationale for Study Design

The ability to manipulate the human gut microbiome and alter mucosal and systemic immunity remains a central question in the study of IBD. We have previously completed a pilot study for FMT at Weill Cornell and have the clinical research infrastructure and clinical expertise to recruit patients, characterize their response, and complete the data analysis. Work from our lab and others has defined the role for specific bacteria in inducing immune responses in mouse models. We also have defined diagnostic signatures of microbial profiles associated with inflammatory disease phenotype in humans

including rheumatoid arthritis and IBD. Emerging clinical data provides evidence for the clinical efficacy of FMT in patients with ulcerative colitis (UC). Preliminary data from our own research suggests that engraftment and/or particular microbial species correlate with clinical outcome, however the factors that determine microbial engraftment are not well defined. Therefore, we designed a randomized, double-blind, placebo-controlled study to examine the possibility of improving the clinical outcome and microbial engraftment of FMP250 by using prebiotic fiber supplementation in active UC patients. Study subjects will be randomized into three groups: (1) *FMP250+Fiber*, (2) *FMP250-Fiber*, and (3) *PlaceboFMP250 with or without Fiber*. Given that fiber alone has not shown significant benefits previously in many UC studies²⁷, we hypothesize that subjects given *PlaceboFMP250+Fiber* will allow us to assess the placebo rate for FMT (*FMP250only* vs. *PlaceboFMP250+Fiber*). Also, considering that we will utilize single donor FMP250 samples, comparing subjects given *FMP250only* and *FMP250+Fiber* will allow us to scientifically assess primary endpoints of the impact of prebiotic supplement on engraftment and efficacy. *PlaceboFMP250-Fiber* will remove any risk of unblinding and will maintain the integrity of our double blinded study.

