6.1.2 Treatment Phase

Eligible subjects will be randomly assigned to one of the three (Placebo or Investigational FMP250 +/- Psyllium) treatment groups. A series of randomized blocks of fixed size will be generated with a 1:1:1 allocation ratio. This will provide assurance that after a given block has completed subject enrollment, there will be the same number of subjects assigned to each of the three study arms.

Treatment assignment will be done during the screening visit because participants randomized to receive fiber supplementation must be provided two psyllium bottles to begin consumption 3 days prior the colonoscopy.

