7.1 Study Intervention/Device Description

7.1.1 Investigational and Placebo FMP250

The proposed intervention will deliver 250 milliliters of FMP250 by colonoscopy to the investigational FMP250 treatment groups at day 0. The placebo treatment group will instead receive the placebo FMP250 by colonoscopy at day 0 and then the investigational FMP250 by flexible sigmoidoscopy at week 8.

Investigational FMP250 is biologically active human fecal material that is pre-screened, tested, quarantined, stored, packaged, and labeled by OpenBiome. Placebo FMP250 is a control unit made of glycerol, saline, and food dye that is stored, packaged, and labeled identically to the investigational FMP250, to ensure blinding during delivery. Weill Cornell Medicine has contracted OpenBiome to supply 135 investigational FMP250 and 135 Placebo FMP250 directly to the [name] laboratory at Weill Cornell Medicine over the course of the study.

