7.4.4 Product Labeling and Documentation

OpenBiome's IB indicates that each sample bottle is labeled with (1) the handling and storage warnings, (2) a lot number and (3) the expiration date based on the storage temperature (pictured below from left to right). The lot number is formatted as XXXX-YYYY-ZZ, where XXXX is the donor number, YYYY is the donation number, and ZZ marks the bottle number. Additionally all donor screening results will be provided in the stool shipment. Released placebo units are affixed with the same label as active FMP250 units, though the specialized lot numbers will allow for differentiation.

[figure not shown]

NOW® Foods brands each Psyllium Husk Powder, Organic plastic bottle with the following label. The label provides nutritional facts, suggested usage, ingredients, and a bar code for commercial use in addition to other details. The lot number and the expiration date are printed at the bottom of each individual unit (not pictured below).

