7.13 Study Intervention/Follow-up Compliance

Adherence to the protocol can be assessed and verified from logs, such as eligibility checklists and standard operating procedures (SOPs), that will be created by study coordinators and confirmed by the treating clinician throughout the course of the intervention. These logs will be based on the schedule of events detailed in **Section 6.1, Table 1.** to ensure the subject's compliance and that all data collection is successfully completed and reviewed at each visit. These paper forms will be stored in each subject's study binder.

In our previous pilot study, we also utilized single colonoscopic delivery of FMP250 and did not experience any loss to follow up due to our short-term follow-up clinic evaluation at 4 weeks post-FMT. Therefore, we anticipate our loss to follow-up rate to remain consistent in this new clinical trial. Considering patients will be blinded up until all study subjects complete week 8 evaluations, we expect them to comply with our follow-up clinic visits because the subject would want to ensure they received the investigational drug. However, if a patient does not respond after three contact attempts (either phone call and/or e-mail) by the study coordinator they will be labeled as a lost to follow-up.

In regard to safety-phone calls at 6-months and 1-year, subjects will be contacted three times (either phone call and/or e-mail). Should subject fail to answer, the investigator or designee will mail a certified letter to the subject's last known mailing address in order to regain contact.

8. Study Intervention Discontinuation and Participant Discontinuation/Withdrawal

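### Fiber assignment is open to the subject, so the unqualified double-blind claim is wrong for the one planned difference in the primary comparison; separately, site staff hold the full allocation list

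*Combined protocol and SAP*

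**What the plan says.** **The blinding claim.** The synopsis describes "A double-blind, randomized, placebo-controlled clinical trial examining the efficacy and safety of Fecal Microbiota Transplantation (FMT) and high fiber supplementation". Section 3.1 repeats "Double-blinded, randomized, placebo-controlled clinical trial" with no qualification. Section 6.1.1 lists "Treatment Randomization (blinded to clinician and subject" as a screening step, and the sub-item beneath it deals with giving psyllium to the fiber groups. Section 3.2 says that the placebo-FMT-without-fiber subgroup "will remove any risk of unblinding and will maintain the integrity of our double blinded study".

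**What is supplied.** Under 6.1.2, "participants randomized to receive fiber supplementation must be provided two psyllium bottles to begin consumption 3 days prior the colonoscopy". Under 7.4.4 the manufacturer "brands each Psyllium Husk Powder, Organic plastic bottle with the following label". The only placebo described is in 7.1.1 and 7.4.2: "Placebo FMP250 is a control unit made of glycerol, saline, and food dye that is stored, packaged, and labeled identically" to the active unit. No placebo powder, over-labelling or masked dispensing of psyllium is described.

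**The primary comparison and endpoint.** Section 12.1 compares FMT plus psyllium with FMT alone by chi-square test. Under 3.1 both arms have the same FMT sequence: active at day 0, placebo at week 8. Clinical response (10.1.1.1, 12.4.1) is a Mayo-score reduction that must include a fall of at least 1 point in the rectal bleeding sub-score.

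**Clinicians.** Sections 3.1 and 7.12 state that clinicians are blinded when they assess response at week 8.

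**Allocation.** Section 7.12 gives the list of randomized blocks to site staff, called study coordinator, research coordinator and research assistant in the same paragraph. Section 4.6 makes clinical research personnel responsible for recruitment, screening, enrollment and allocation. Assignment is made at screening, before day-0 endoscopic eligibility (6.1.2), and randomized subjects who are not treated may be replaced (8.2).

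**The concern.** A subject who is handed labelled psyllium, or nothing, knows the fiber assignment. In the primary comparison that knowledge separates the two arms completely. Stool frequency and rectal bleeding are reported by the patient, and the physician's global assessment draws on the patient's recollection, so expectation can reach the endpoint even if the scorer stays blinded. Section 15 presents the trial as meant to be definitive on fiber supplements, and the synopsis attaches the double-blind label to fiber as well as FMT. A reader could give the fiber result the weight of a double-blind comparison, which it is not.

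The second issue is smaller. Whoever holds the full list can see future assignments. Because assignment precedes final eligibility and untreated subjects may be replaced, a leak could affect who stays in the trial.

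**Working it through.** **1. What the placebo-without-fiber subgroup protects.** Inputs (3.1): 45 per arm, Group 3 split in half by fiber.
- Fiber takers: 45 on active FMT plus about 22.5 on placebo FMT. P(active FMT) = 45/67.5 = 0.667.
- Non-takers: the same counts, so again 0.667.
- With a whole-number split of 22 and 23 the two values are 45/67 = 0.672 and 45/68 = 0.662.

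Fiber status tells a subject almost nothing about FMT, so the FMT blind is protected. The subgroup does nothing to hide fiber status itself.

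**2. Fiber within the primary comparison.** Group 2 (45) all take psyllium and Group 1 (45) take none. With the same FMT sequence in both, 90 of 90 subjects know the one factor on which the arms are planned to differ.

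**3. Route to the endpoint.** Stool frequency (0–3) and rectal bleeding (0–3) make up 6 of the 12 Mayo points. The bleeding fall is a necessary condition for response. Psyllium starts on day -3, so the day-0 and week-8 scores are both taken with fiber status known to the subject.

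**4. The plan's own power figure.** Inputs (12.1): 55% v 27%, 45 per arm, two-sided 0.05, about 80% power.
- Unpooled sample size: n = (1.960 + 0.842)² × (0.55×0.45 + 0.27×0.73) / 0.28² = 7.849 × 0.4446 / 0.0784 = 44.5, rounded up to 45. This reproduces the plan.
- Pooled-variance power at 45 per arm: Φ[(0.28×√45 − 1.960×√(2×0.41×0.59)) / √0.4446] = Φ(0.772) = 78.0%, consistent with about 80%.

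**5. Illustration of bias (the shifts are assumed; the documents give none).** Exact enumeration of the uncorrected chi-square test, 45 per arm, true response 27% in both arms, with a net shift toward fiber added to the FMT plus psyllium arm:

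| Assumed shift | Rejection rate | of which in favour of fiber |
|---|---|---|
| 0 | 5.4% | 2.7% |
| +5 points | 8.6% | 7.9% |
| +10 points | 18.1% | 18.0% |
| +15 points | 33.1% | 33.1% |

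With a true rate of 20% or 35% in both arms, a 10-point shift gives 20.3% or 15.8%.

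The opposite direction is also possible. If the true rates are 55% v 27% and expectation takes a net 10 points off the fiber arm, the comparison is 45% v 27%. Power is then Φ[(0.18×√45 − 1.960×√(2×0.36×0.64)) / √(0.45×0.55 + 0.27×0.73)] = Φ(−0.184) = 43%, against 78%.

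**6. What keeps fiber status from the scorer.** Clinician blinding is stated, but no step is described that delivers it for fiber. Week 8 includes a medication history (6.1.2.2). Protocol-adherence logs based on Table 1, which has a psyllium row, are "created by study coordinators and confirmed by the treating clinician throughout the course of the intervention" (7.13). Under 6.1.1 a fiber subject's baseline research sample should be taken before day -3, so one first taken on day 0 would suggest no fiber. The documents do not say whether the treating clinician and the scorer are different people.

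**The case against.** **6.1.1 may be meant for FMT only.** Table 1 labels the FMP250 rows as blinded but not the psyllium row, 3.1 names FMP250 as the study drug, and the handing-out of psyllium is disclosed. Full arm identity also stays masked, since a fiber taker may be in Group 2 or 3. This reading is fair for 3.2 and 7.13, which need only say that they mean FMT. It does not rescue 6.1.1, where the line covers the whole assignment and its sub-item is fiber, or the synopsis, which names fiber.

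**A reader might infer that clinicians are in fact unblinded to fiber.** The documents do not show that. The coordinator keeps the psyllium log (7.3), 3.1 calls the week-8 scoring independent, no psyllium-intake log is described, and it is not stated that the medication history records a dietary supplement. What stands is that no safeguard is described.

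**A reader might infer that the bias must favour fiber.** It need not. Expectation could already lower the day-0 score and make the required fall harder to reach.

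**A reader might infer that the list-holder recruits or judges eligibility.** Section 4.6 puts recruitment and allocation in one staff group but does not name the list-holder. Block size is hidden from investigators (3.1), and a clinician confirms day-0 endoscopic eligibility (7.8.1).

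**The plan has some supporting evidence.** It compares placebo FMT with and without fiber, and it collects endoscopic response, calprotectin and CRP. The first has about 22 v 23 subjects and cannot separate expectation from a true effect. The others depend less on patient report but are not the primary endpoint.

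**Conclusion.** **(a) Wrong as written, high confidence.** The trial as described is double-blind for FMT and open to the subject for psyllium. The statement in 6.1.1 and the unqualified labels in the synopsis and 3.1 are therefore incorrect for fiber. This affects all 90 subjects in the primary comparison and an endpoint with a compulsory patient-reported component. The conclusion rests on the supply and placebo descriptions, not on any bias figure. The rejection rates and the reduced power are illustrations under assumed shifts; the actual size and direction are unknown.

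**(b) Cheap improvement, moderate confidence.** Giving the full block list to site staff, in a group that also recruits and screens, leaves future assignments visible to the list-holder. The documents do not show that this person selects subjects.

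**What to change.** **Wording.** In the synopsis, 3.1, 3.2, 6.1.1 and 7.13, state: *double-blind for FMT; open to the subject for psyllium; assessor intended to be blinded to fiber*. In section 15, qualify the claim of definitive evidence as it applies to fiber.

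**Scoring order.** At day 0 and week 8 the scorer completes and locks the Mayo score before seeing the medication history or any other record that shows fiber status. Existing staff can do this. Adverse event and safety reporting stays unrestricted throughout.

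**Allocation.** The statistician releases each assignment singly, after consent and screening eligibility are recorded. REDCap could do this if its randomization function is confirmed, since 11.1.1 describes it only as a data-capture system. Released assignments stay available to the coordinator for emergency unblinding under 7.12. Report by arm, with the reason, every subject randomized but excluded or replaced on or before day 0.

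**Cost.** A less favourable blinding statement, a fixed order of steps at two visits, and a little statistician or set-up time. No patient procedure is added. The patient-reported items remain open to expectation, because none of these changes hides fiber status from the subject.
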